Statistical Analyses and Power Estimation: As a pilot feasibility study with double-blind crossover design, the design affords greater power and need for enrollment of fewer subjects. Similar design with this medication has suggested sample size of 40 was sufficient for effect sizes typically observed with this medication in similar populations (Bain et al 2013). To account for patient dropouts, the study will enroll/consent up to 50 patients. This will ensure 40 subjects complete the entire study. This design will allow initial pilot feasibility data, improved control and testing of causation, and greater power in the allotted time-frame and funding level. The primary consideration is difference in outcome between baseline and endpoint with ATX treatment as compared to placebo. The primary outcome measure a priori will be the change in total CAARS-S:S scores, AAQoL-29 and BAARS-IV. Secondary measures include the remaining efficacy and safety measures as delineated above. The primary outcome of interest is the moderating impact of ATX treatment (medication \times ADHD TAU) on treatment response (pre- and post-treatment measures of cognitive symptoms of ADHD and PTSD, functional impairment in daily living domains, and global functioning). A mixed model, repeated-measures multivariate analysis of variance with pre- and post-ADHD TAU treatment ADHD symptoms, functioning, and global functioning entered as repeated measures; and ATX treatment entered as the between factors. Pre-treatment PTSD severity scores (CAPS) will also be entered into the model as a potential explanatory covariate. Simple slopes using repeated measures ANOVA will be used to probe significant interactions

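### The planned model enters ATX as a between-patient factor in a crossover, and the two primary-outcome statements need reconciling under one stated alpha and success rule

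*Combined protocol and SAP*

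**What the plan says.** All of the following is in section C3, Statistical Analyses and Power Estimation, unless noted.

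- **Contrast:** "The primary consideration is difference in outcome between baseline and endpoint with ATX treatment as compared to placebo".
- **First primary statement:** "The primary outcome measure a priori will be the change in total CAARS-S:S scores, AAQoL-29 and BAARS-IV". The next sentence makes the remaining efficacy and safety measures secondary. C3, Efficacy Assessments and Outcome Measurement, names the same three scales in its primary-outcome sentence and lists CAPS among the secondary assessments.
- **Second primary statement:** "The primary outcome of interest is the moderating impact of ATX treatment", written as medication by ADHD TAU and applied to pre- and post-treatment "measures of cognitive symptoms of ADHD and PTSD, functional impairment in daily living domains, and global functioning".
- **Model:** a repeated-measures MANOVA with "pre- and post-ADHD TAU treatment ADHD symptoms, functioning, and global functioning entered as repeated measures" and "ATX treatment entered as the between factors". Then: "Pre-treatment PTSD severity scores (CAPS) will also be entered into the model as a potential explanatory covariate". Follow-up is given as "Simple slopes using repeated measures ANOVA will be used to probe significant interactions".
- **Design (C1, Overview):** a two-sequence crossover in which one group takes ATX then placebo and the other placebo then ATX. Patients are unblinded after crossover, and the data are then cleaned and analysed.
- **Objectives (C1):** the Primary Objective adds treatment retention to cognitive symptoms and functional impairment. Broad PTSD symptoms are the Tertiary Objective.

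Neither the statistical section nor any other part of the document states an alpha, sidedness, success rule or multiplicity control. ADHD TAU is not defined and is no arm or row of Table 1. Global functioning is tied to no scale.

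**The concern.** **Model and design.** In this crossover the treatment comparison lies within patients. A between-patient treatment factor compares the two conditions as if different people supplied them. The stable differences between patients, which the crossover is meant to remove, then stay in the error term. The section names no period or sequence term either. The design was chosen for its power with few patients, and the model as written gives that advantage away.

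**What is being claimed.** Two statements carry the primary label, and their lists differ. Retention, in the Primary Objective, is in neither. With no rule saying which term or scale decides, the choice could be made after unblinding. C4 expects the primary objective to be met, and C5 presents the trial as a possible platform for large-scale studies, so a reader will want to know what counted as success.

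**Working it through.** **1. The plan's own figure.** The plan gives 40 completers and up to 50 enrolled. 40 / (1 - 0.20) = 50, which fits a 20% dropout rate that is not stated. The 40 itself cannot be rederived, because no alpha, power, effect size or SD is given. For scale only: one paired test at two-sided 5% and 80% power detects (1.960 + 0.842) / √40 = 0.44 SD of the within-patient difference (0.45 with the t distribution).

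**2. Between-patient against within-patient analysis.**

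Inputs: 40 completers (plan); 20 per sequence, two-sided 5%, an effect of 0.45 SD of the within-patient difference, and within-patient correlation ρ between the two period values of 0.3, 0.5 or 0.7 (all assumed).

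- Let σ be the SD of one period value. The true standard error of the mean difference is √(2σ²(1 - ρ)/40). A between-patient model uses √(2σ²/40). The ratio of true to used is √(1 - ρ) = 0.837, 0.707, 0.548.
- The critical value on 78 df is 1.991. In true units the test therefore rejects only beyond 1.991/√(1 - ρ) = 2.38, 2.82, 3.63.
- The signal is 0.45 × √40 = 2.846. Approximate power is Φ(2.846 - 2.38) = 68%, Φ(2.846 - 2.82) = 51%, Φ(2.846 - 3.63) = 22%.
- Simulation, which lets the variance estimates vary, gives the figures below.

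| Analysis | ρ = 0.3 | ρ = 0.5 | ρ = 0.7 |
|---|---|---|---|
| Within-patient, period-adjusted (38 df): power | 79% | 79% | 79% |
| Period values as independent: power | 68% | 52% | 23% |
| Period values as independent: actual level of the nominal 5% test | about 2% | 0.6-0.7% | 0.05-0.06% |

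With positive ρ the error is towards missing an effect, not towards false claims.

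**3. The two primary statements side by side.**

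| | First statement | Second statement | Model |
|---|---|---|---|
| ADHD symptoms | CAARS-S:S, BAARS-IV | yes, no scale named | yes, no scale named |
| Functioning or quality of life | AAQoL-29 | daily-living impairment | functioning |
| PTSD | no | within the phrase on cognitive symptoms | baseline CAPS as covariate only |
| Global functioning | no | yes, no scale named | yes, no scale named |
| Retention | no | no | no |

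If ADHD TAU is only a pre/post label, as its use in the model suggests, medication by time is the ATX versus placebo difference in change. That is the stated primary consideration and can be estimated.

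**4. Multiplicity (secondary).** Assumptions: two-sided 5% per test, three scales with equal correlation from 0 to 0.9, no true effect. With independent scales, any one of three gives 1 - 0.95³ = 14.3%. The other figures come from simulated crossovers (20 + 20 completers, t-tests on 38 df, Hotelling T² on 3 and 36 df).

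| Rule | False-positive chance, correlation 0 to 0.9 |
|---|---|
| One named scale | 5% |
| One multivariate test | about 5% |
| All three scales required | 0.01% to 2.2% |
| Any one scale suffices | 14.3% down to 8.5% (favouring ATX only: about 7.3% to 4.2%) |

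These figures compare decision rules for the three scales. They do not measure the conflict between the two primary statements.

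**The case against.** **The two statements can be read together.** The first names instruments and the second names an effect. The words a priori, the sentence making remaining measures secondary, and the matching list under Efficacy Assessments all favour the three scales. C4 supports its optimism with ADHD symptoms, cognitive function and quality of life, not PTSD symptoms. This largely stands: the wording needs reconciling, but the documents are not evenly split.

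**A reader might infer that PTSD symptoms are promoted to primary.** The documents do not support this. The phrase can mean cognitive symptoms in both conditions. The broad PTSD spectrum is a separate, tertiary objective, and the model uses CAPS only as a baseline covariate.

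**A reader might infer a false-positive rate of up to 14%.** That needs an any-one-scale rule, which is stated nowhere. The scales are joined by *and*, and the only named model is multivariate. The figure also counts results favouring placebo.

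**The between label may be loose wording.** An analyst who fits a patient effect would recover the within-patient contrast, and the CAPS covariate would absorb some between-patient variance. This is possible, but the text says between and does not specify a patient, period or sequence term. The losses shown are for the literal reading.

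**It is a pilot.** That lowers the stakes. It does not remove them, because the Primary Objective is efficacy against placebo.

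**Conclusion.** The point holds in this form. The model as written does not match the crossover, and that is the firmest part because it rests on the text alone. Its size is illustrative: at the assumed correlations, power falls from about 79% to between 68% and 23%. The 0.45 SD effect was chosen because it is about what 40 completers can detect at 80% power, so 79% is not an estimate of this trial's power.

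The second primary statement must be reconciled with the three scales, and the absence of an alpha and success rule is a real gap. Depending on the rule, the false-positive chance is at most about 2%, about 5%, or 8-14% (about 4-7% favouring ATX), under the assumed alpha and correlations. The ADHD TAU term is a wording defect; a reader might infer that the contrast is untestable, but the pre/post reading makes it estimable. This should be fixed, with the model first and multiplicity second.

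**What to change.** Make a dated amendment before any treatment codes are released, and before the first release if patients are unblinded one at a time.

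1. **Model.** Replace the between factor with a within-patient ATX versus placebo factor, adjusted for period. Replace the medication-by-ADHD TAU wording with that contrast.
2. **Primary set and rule.** State that the three scales are the primary set and fix one rule at two-sided 5%. Either test CAARS-S:S total first (W5 against W10), then the other two in a stated order; or use one within-patient multivariate test of the three as gate, followed by Holm-adjusted single-scale tests. Table 1 has all three scales at W5 and W10. If baseline means the single screening visit it cancels: (Y_ATX - B) - (Y_PBO - B) = Y_ATX - Y_PBO.
3. **Other domains.** Keep CAPS outcomes secondary. Drop global functioning from the primary model unless it is tied to a scale measured the same way before and after; CGI-S is taken at baseline only.
4. **Retention.** Reconcile the Primary Objective with the outcome list. Appointment attendance (C3, Safety assessments) is recorded as a compliance measure and may not capture retention in PTSD treatment, so do not assume that it can serve.

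**Cost.** Items 1 to 3 need an amendment but no new visits or data. The three scales can no longer each carry the claim alone. In the illustration (0.45 SD on every scale, correlation between scales 0.5 to 0.9), power is 79% for CAARS-S:S first and 80% down to 65% for the multivariate gate. An any-one rule would have 95% down to 87%. If the CAARS-S:S effect were 0.3 SD, its power would be 46%.

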impairment and treatment retention are both improved, while **The Secondary Objective** is to replicate the our preliminary finding of negative impact of cognitive symptoms of ADHD on PTSD clinical outcomes. **The Tertiary Objective** is to assess the efficacy of ATX in reducing broad spectrum of PTSD symptoms. The proposed study will take 10 weeks and include two phases (**Phase I**: Initial Phase, 5 weeks; **Phase II**: Crossover Phase, 5 weeks). The crossover design was employed to both achieve study objectives while minimizing costs. Each phase consists two periods: **Period I** (week1 in Phase I and week6 in phase II) consist of psychological and physical assessments and placebo lead-in/wash-out, in which subjects take 6 days placebo; **Period II** (weeks 2-5 in Phase I and week7-10 in Phase II) consist of treatment with either atomoxetine 80mg daily or placebo daily). This project will take advantage of established on-going PTSD assessment and treatment clinical trials currently performed at the Ralph H. Johnson VA Medical Center (RHJVAMC) to facilitate recruitment. The proposed 50 veterans with ADHD/PTSD will be recruited from these on-going trials enabling both comprehensive assessment and evaluation of patients' engagement in ongoing PTSD treatments. Subjects will be randomized and assigned by the study investigator ([name]) into crossover group 1 (ATX at Phase I, then placebo at Phase II) or 2 (placebo at Phase I, then ATX at Phase II) with both placebo and medication administered through pharmacy. Subjects and other investigators are thus able to remain blinded to the order of treatment assignment throughout the study. The 1-week interval was based on published pharmacokinetic data for 4 week doses of ATX (*Witcher et al, 2003*). After crossover, patients will be unblinded and data will be cleaned and analyzed. Final follow up will be 30-days after last visit.

C2. Investigational Agent: ATX is a non-stimulant, FDA approved agent for treatment of ADHD. ATX 80mg is the most common adult dose used in ADHD with and without comorbid condition (Adler et al, 2009). In this project, 80 mg ATX and placebo will be prepared in capsules with identical appearance and similar taste by Eli Lilly and Company, Indianapolis, Indiana.

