PTSD Medication Stabilization: Those patients meeting inclusion criteria will be asked to maintain medications at current dosages where medically possible. Participants who have not initiated new prescription medications in the previous 4 weeks will initiate treatment one week following the assessment battery. However, those potential participants who have recently begun trials of prescription medication will be required to wait 4 weeks post-assessment to ensure medication stabilization, at which point the assessment battery will be re-administered.

Efficacy Assessments and Outcome Measurement: Primary outcome measures will be conducted at baseline and all subsequent visits by a qualified research clinician using the CAARS-S:S, with the Barkley Adult ADHD Rating Scale-IV (BAARS-IV) and Adult ADHD Quality of Life-29 (AAQoL-29) conducted at follow up visits. Clinical Global Impression Severity (CGI-S, at baseline only) and Clinical Global Impression Improvement (CGI-I, at all visits except baseline and W1) will be done as well. Additional assessments for evaluating secondary outcomes will include the Clinician Administered PTSD Scale (CAPS), Hamilton Depression Scale (HAM-D). Quality of life will be assessed using the Veteran's version of the Medical Outcomes Study 36-Item Short-Form Health Survey (SF36-V). In addition to subjective measures, the response inhibition task Go/NoGo (GNG) and Stop Signal (SST) will be used as objective assessments to measure ATX treatment outcomes.

Key Assessment Measures:

Mini-International Neuropsychiatric Interview (MINI, Sheehan et al., 1998): The MINI is an abbreviated structured psychiatric interview that takes approximately 10-20 minutes to complete. The MINI has shown good inter-rater reliability and test-retest reliability for screening psychiatric disorders.

CAADID Part II: Diagnostic Criteria (CAADID, Epstein et al., 2001) The CAADID is a structured interview that assists in the process of diagnosing adult ADHD. This assessment is appropriate for those 18 and older. It is most effective when used with other types of ADHD measures, such as the CAARS™.

Clinician Administered PTSD scale (CAPS, Weathers et al., 2000): The CAPS is a structured interview that assesses both frequency and intensity of PTSD symptoms according to DSM-IV criteria. It provides both a dichotomous index for PTSD diagnoses and a continuous index of PTSD symptom severity.

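### A change-score primary outcome with undefined phase baselines, and ATX entered as a between factor, gives up within-patient precision that the crossover already provides

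*Combined protocol and SAP*

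**What the plan says.** Three sentences under Statistical Analyses and Power Estimation (C3) fix the analysis. The outcome: "The primary outcome measure a priori will be the change in total CAARS-S:S scores, AAQoL-29 and BAARS-IV". The contrast: "The primary consideration is difference in outcome between baseline and endpoint with ATX treatment as compared to placebo". The model is a mixed, repeated-measures multivariate ANOVA in which pre and post scores are the repeated responses, with "ATX treatment entered as the between factors". The ATX effect is therefore an ATX-by-time interaction, that is, a difference between changes. One covariate is named: "Pre-treatment PTSD severity scores (CAPS) will also be entered into the model as a potential explanatory covariate". No patient, sequence or period term is named, and nothing says which visit supplies the baseline for each phase.

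On data collection, the efficacy section of C3 states: "Primary outcome measures will be conducted at baseline and all subsequent visits by a qualified research clinician using the CAARS-S:S". Table 1 agrees, with CAARS-S:S at Screening/Baseline, W1, W2, W5, W6, W7, W10 and W14. BAARS-IV and AAQoL-29 are taken at Screening/Baseline, W5 and W10 (BAARS also at W14), so neither has a phase-start score for Phase II. CAPS is taken at Screening/Baseline, W5 and W10.

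**The concern.** Every completer receives both ATX and placebo, so comparing the W5 and W10 scores already removes that patient's stable level. Subtracting a separate starting score in each phase adds the noise of two further measurements. It pays for itself only if the start and end of a phase are much more alike than scores from different phases. Entering ATX as a between factor can also set aside the pairing itself.

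Precision is at stake. The plan justifies 40 completers by the greater power of a crossover, and it gives no effect size, SD, alpha or target power that would show room to absorb a loss. The phase-start CAARS-S:S scores, which could sharpen the estimate as covariates, are collected but given no such role.

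**Working it through.** **The plan's own figure.** The 40 completers cannot be reproduced, because the number is carried over from a similar trial without alpha, power, effect size, SD or correlation. The 50 enrolled implies 20% dropout (40/50 = 0.80). Everything below is therefore relative, and assumes two-sided 5% tests and scores of equal variance s².

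**Own-phase change (CAARS-S:S only).** Let B1, Y1, B2, Y2 be the start and end scores of the two phases, all with pairwise correlation r.

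- End scores: Var(Y1 − Y2) = 2s²(1 − r).
- Changes: Var[(Y1 − B1) − (Y2 − B2)] = 4s²(1 − r).
- Ratio: 2 for any r.

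Now let the within-phase correlation be rw and every between-phase correlation rb, and put θ = (rw − rb)/(1 − rb). Relative to end scores, the change contrast has variance 2(1 − rw)/(1 − rb) = 2(1 − θ). The end-score contrast adjusted for B1 − B2 has 1 − θ² = (1 − θ)(1 + θ). Since 1 + θ cannot exceed 2, adjustment is never worse than subtraction.

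| rw | rb | change / end | adjusted / end |
|---|---|---|---|
| 0.5 | 0.5 | 2.0 | 1.00 |
| 0.6 | 0.5 | 1.6 | 0.96 |
| 0.7 | 0.5 | 1.2 | 0.84 |
| 0.75 | 0.5 | 1.0 | 0.75 |
| 0.8 | 0.5 | 0.8 | 0.64 |

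Under correlation that decays by week (assumed weekly values 0.98 down to 0.80), the change ratio is 1.68 to 2.17 with W1/W6 as phase start and 1.26 to 1.68 with W2/W7.

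**Power for that case.** With 40 completers and 38 df, 80% power needs a noncentrality of 2.875. Doubling the variance gives 2.875/√2 = 2.03, hence 51%. A design with 90% power falls to 63%. Roughly 80 completers (2 × 40) would restore the loss.

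**One screening score for both phases.** (Y1 − B0) − (Y2 − B0) = Y1 − Y2, so the ratio is 1.00 within patient. If ATX is a between factor and the two changes are treated as independent, the variance used is 2 × 2s²(1 − r) = 4s²(1 − r), although the true variance is 2s²(1 − r). Under equal correlation, power is about P(Z > 1.99√2 − 2.875) = P(Z > −0.06) = 52%. Under the weekly decay above it falls to between 44% (weekly 0.80) and 30% (0.98).

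**All forms together.** In simulation at N = 40, with the effect set to 80% power on paired end scores:

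- end scores adjusted for the phase-start difference: 78 to 93%;
- own-phase change, within patient: 51 to 88%;
- own-phase change, ATX as a between factor: 52 to 89%;
- change from screening, ATX as a between factor: 31 to 53%.

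**W5 as the Phase II baseline.** This is the only Phase II alternative to screening for BAARS-IV and AAQoL-29. The contrast becomes 2·Y1 − B0 − Y2, with variance 6s²(1 − r), three times that of end scores. It also misstates the effect. If ATX has its full effect d by W5, patients given ATX first contribute d − (−d) = 2d and patients given placebo first contribute d, so the average is 1.5d.

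**CAPS.** A screening value is constant within a patient and cancels from the paired contrast. Simulated change/end ratios were 2.09 to 2.12 with CAPS in the model and 2.00 to 2.07 without. In the between-factor form it could explain (0.497 − k)²/[2(1 − r)] of change-score variance, where 0.497 is the CAPS-CAARS correlation in B2.1 and k is its assumed correlation with the endpoint. With k = 0.2 and r = 0.7 this is 0.088/0.6 = 15%, and it is smaller elsewhere in the range tried. Undoing a doubling would need 50%.

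**The case against.** A reader might infer that the plan prescribes change within each phase, that the variance therefore doubles, and that the trial has 51% power. The documents do not support this. Table 1 and C3 use the word baseline for the single screening visit, and that is the only baseline that all three primary scales share. On that reading the baseline cancels within patient. Doubling is also only the equal-correlation case: subtraction costs nothing once rw reaches 0.75 with rb at 0.5. All of this stands, and the power figures are conditional illustrations.

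A second objection is that the model as written is not paired. With ATX as a between factor, end scores have no advantage over changes: simulated power was 52% against 51% at r = 0.5, 24% against 51% at r = 0.7, and 8% against 51% at r = 0.8. This also stands, as a warning that the outcome and the model must change together. It does not remove the gain, because the paired, adjusted analysis did better than each form tried. The phrase mixed model might be meant to include a patient effect, in which case the between-factor loss would not arise. But no such term is named, and the stated role of ATX points the other way.

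Third, adjustment can do harm if the phase-start score is taken on treatment. C1 puts treatment in weeks 2 to 5 and 7 to 10, whereas Table 1 labels W1/W6 as phase start and W2/W7 as treatment visits. If half the drug effect were already present at W2/W7 (assumed), an adjustment slope of 0.27 to 0.37 would bias the estimate down by about 13 to 18%. This stands, and the fix is conditional on timing.

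Finally, a reader might infer that a W5 CAPS covariate would bias the estimate. The plan says pre-treatment, and W5 is not pre-treatment for patients given ATX first, so that use cannot be read into it.

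**Conclusion.** The point holds as a loss of precision, not as an invalid analysis. The plan leaves the phase baselines undefined, analyses change, and enters ATX as a between factor, so within-patient information goes unused on either reading of baseline. With own-phase baselines (CAARS-S:S only) the contrast variance is 2 times that of end scores under equal correlation, about 1.3 to 2.2 times under serial decay, and no greater when within-phase correlation is high. With a screening baseline there is no inflation from the baseline, and the loss comes from the between-factor form. The corresponding falls from 80% power are to about 51% (equal correlation) and to about 30 to 53%. They rest on assumed correlations and on an assumed 80% starting point, since the documents supply neither. Screening CAPS does not recover the loss. In a pilot this does not threaten the trial, but the remedy uses data already scheduled.

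**What to change.** - For each primary scale, define the primary estimate as the within-patient ATX minus placebo difference in phase-end scores (W5 and W10), from a model with treatment and period effects and with patient (or sequence) accounted for.
- For CAARS-S:S, enter the difference between the two phase-start scores as a covariate and do not subtract it. Use only scores taken before the first treatment capsule of each phase. W2 and W7 qualify if the scale is completed at dispensing. Confirm this against Table 1, which labels W1 and W6 as phase start, and state the timing in the SAP.
- Do not use W5 as the Phase II baseline for BAARS-IV or AAQoL-29.
- Use CAPS only as the Screening/Baseline value, as a possible modifier of the ATX effect.

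The cost is SAP wording and one degree of freedom, about 1 point of power if the phase-start difference turns out to be uninformative. No visit or assessment is added.

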
A2. Review of the Literature Relevant to This Application

Cognitive Impairments in Comorbid ADHD/PTSD: Combat Veterans with PTSD often show cognitive impairments in attention, working memory, executive functions, and inhibitory control (Vasterling, 2007), a cluster of symptoms overlapping with symptoms of adult ADHD. It has been proposed that the cognitive deficits in PTSD may be related to the same disturbance of fronto-temporal systems observed in ADHD. This hypothesis has been supported by several imaging research findings that indicate functional alteration in the medial frontal and lateral prefrontal cortex in PTSD (Nee et al 2007, Shin et al 2006). Further, impaired response inhibition task, Go-NoGo (GNG), a measure of executive function has been observed both in ADHD and in PTSD patients (Fisher et al 2011; Swick et al 2012). Finally, there is substantially higher rates of PTSD development in individuals with ADHD (Hanson et al 2012), suggesting that both may share common biological risks. Although the exact mechanisms of co-occurrence of cognitive symptoms in both ADHD and PTSD is not yet fully known, research has suggested that this cognitive impairment plays an important role in PTSD development, treatment response, and prognostic outcomes (Aupperle et al, 2012). **Cognitive Function and PTSD Treatment Outcome:** Many cross-sectional studies have documented strong evidence that PTSD is associated with significant cognitive impairment, and the presence of cognitive impairments is related to poorer treatment outcome (Verwoerd et al, 2009; Wild and Gur, 2008; Walter et al, 2010). As a result, the DSM-5 diagnostic criteria for PTSD have expanded the cognitive symptom criteria associated with PTSD. In the past 2 decades, extensive psychological and pharmacological treatments have been developed for PTSD, but as many as 50% of individuals with PTSD do not fully respond to the standard interventions and drop-out rates are often cited around 30%. Many of these standard treatments are developed predominantly to address re-experiencing and avoidance symptoms, but not cognitive impairment. However, in patients with PTSD, the impairment in occupational, academic, and social functioning often persists after receiving specialized treatment, including successful treatment of PTSD symptoms of avoidance and re-experiencing (Westphal et al, 2011). It is well documented that intact cognitive function is essential for activities of daily living, including self-care. However, problematic treatment behaviors commonly associated with impaired cognitive functioning are not targeted as part

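### The named repeated-measures MANOVA comes with no missing-data rule and would by default drop patients with any missing score; a likelihood-based crossover model should replace it

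*Combined protocol and SAP*

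**What the plan says.** The statistical paragraph of C3 describes the model as "A mixed model, repeated-measures multivariate analysis of variance with pre- and post-ADHD TAU treatment ADHD symptoms, functioning, and global functioning entered as repeated measures", and continues "ATX treatment entered as the between factors". Pre-treatment CAPS is a possible covariate, and significant interactions are to be probed by repeated-measures ANOVA. Three scales share the primary role: "The primary outcome measure a priori will be the change in total CAARS-S:S scores, AAQoL-29 and BAARS-IV".

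The target number comes from a cited study: "Similar design with this medication has suggested sample size of 40 was sufficient for effect sizes typically observed with this medication in similar populations". The paragraph then states "To account for patient dropouts, the study will enroll/consent up to 50 patients" and "This will ensure 40 subjects complete the entire study".

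C1 describes a two-sequence crossover in which each patient takes ATX in one phase and placebo in the other. Table 1 schedules the CAARS-S:S at every visit, the AAQoL-29 at screening, W5 and W10, and the BAARS-IV at those visits plus W14. Section 1.2b of the human subjects part lets patients withdraw whenever they wish. The documents define no analysis population, no missing-data method, no use for scores collected before withdrawal and no sensitivity analysis. For standard PTSD interventions, A2 reports that "drop-out rates are often cited around 30" percent.

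**The concern.** A classical repeated-measures MANOVA needs a full outcome vector from each patient. With several scales entered jointly, one missing scale at one visit is enough to remove a patient. If the vector spans both phases, a patient who finishes Phase I and then leaves is removed together with a valid W5 endpoint on all three primary scales.

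The alternative is to enter each phase as its own pre/post record, with ATX as a between factor. This keeps the Phase I record, but it treats two records from one patient as independent, which is wrong in a crossover.

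Outcome-related dropout is plausible on the protocol's own account. A1 links ADHD cognitive symptoms to poorer attendance, and the primary objective in C1 joins symptom reduction with better retention. The primary scales measure those symptoms, so the patients who leave may differ systematically on the outcome from those who stay.

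**Working it through.** **1. The plan's own numbers.** Implied dropout is 1 - 40/50 = 20%, and 40/(1 - 0.20) = 50, so 50 and 40 agree. No dropout rate is stated, so this is only a consistency check. The figure of 40 cannot be reproduced, because no effect size, SD, alpha or power is given.

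**2. At the dropout rate cited in A2.** 50 x (1 - 0.30) = 35 completers; 40/(1 - 0.30) = 57.1, so 58 would have to enrol for 40 to complete. To give this a scale, assume a paired t-test at two-sided 5%: 40 completers have 80% power for a standardised within-patient difference of 0.454, and 35 have 74% for the same difference.

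**3. What happens to a patient who leaves in Phase II.**
- One vector per patient across both phases: W10 is missing, the patient is deleted, and W5 is lost.
- One record per phase: W5 is kept, but the correlation between the two phases is ignored. With n patients, outcome variance s² and correlation r between the two phase scores, the variance of the treatment difference is 2s²(1 - r)/n; under independence it is taken as 2s²/n. The standard error is then too large by the factor 1/sqrt(1 - r): 1.20 at r = 0.3, 1.41 at r = 0.5 and 1.83 at r = 0.7. The gain from the crossover is thrown away.

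Neither form of the named method is satisfactory.

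**4. Bias of the completers-only contrast, by simulation.** All inputs are assumptions: 2x2 crossover, N = 50, outcome SD 1, true effect -0.45 (negative is improvement), between-patient SD of the effect 0.3, period effect -0.1, r = 0.3, 0.5 and 0.7, 1,500 runs each. The completers' within-patient contrast was compared with a generalised least squares fit to all observed phase endpoints. The dropout rules were:
- (a) 18% per phase on ATX and 5% on placebo, unrelated to outcome;
- (b) the same base rates, but Phase II dropout also depends on the Phase I score (log-odds 1.0 per SD);
- (c) ATX-first patients with a poor Phase I score leave before the Phase II endpoint (base 25%, log-odds 1.5 per SD), against 8% of placebo-first patients and 2% of all patients in Phase I;
- (d) poor responders leave during ATX before that phase's endpoint (base 18%, log-odds 1.5 per SD), with 5% on placebo.

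| Rule | Completers only | All observed endpoints |
|---|---|---|
| (a) | -0.446 to -0.458 | -0.446 to -0.459 |
| (b) | -0.404 to -0.427 | -0.449 to -0.452 |
| (c) | -0.512 to -0.581 | -0.449 to -0.456 |
| (d) | -0.555 to -0.660 | -0.587 to -0.692 |

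Simulation error of a mean is at most about 0.195/sqrt(1,500) = 0.005. Relative to -0.45, completers in (b) are 5% to 10% too small (0.427/0.45 = 0.949; 0.404/0.45 = 0.898). In (c) they are 14% to 29% too large (0.512/0.45 = 1.138; 0.581/0.45 = 1.291). The all-data fit removes both biases. In (a) neither estimate is biased, and the completers' standard error is 1% to 2% larger (for example 0.195 against 0.191). In (d) both are too large, completers by 23% to 47% and the all-data fit by 30% to 54%. On average about 5 to 10 of the 50 patients had a Phase I endpoint only.

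**The case against.** The strongest reply is that the plan never says incomplete patients are excluded, and that its words mixed model could mean a likelihood-based mixed-effects model, which keeps partial data. The first half stands: case deletion is an inference. The second half is weaker. The sentence names a MANOVA with between factors, follows it with repeated-measures ANOVA, and mentions no random effect, covariance structure or likelihood. If a likelihood model was meant, the same edit makes that clear.

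Several stronger readings are tempting, and the documents do not support them.
- A reader might infer that anyone who leaves after Phase I certainly contributes nothing. The text does not say how the two phases enter the model, and with separate records the Phase I data survive, at the price in step 3.
- A reader might infer that heavier dropout on ATX is enough to bias the result. Rule (a) shows that it is not; dropout must be related to outcome or response, and rules (b) and (c) show that the bias can go either way.
- A reader might expect the analysed sample to shrink to about 22, from 35 x 0.95^9 (0.95^9 = 0.63). That rests on an assumed 5% missing rate in all nine scale-by-visit scores. Three of these are baseline scores, and the CAARS-S:S among them is needed for eligibility. With the six later scores alone, 0.95^6 = 0.735 leaves about 26 of 35 or 29 of 40, still on the assumed 5% and a single joint vector.
- The 30% in A2 concerns standard PTSD interventions. It is not a forecast for this 10-week adjunctive trial.

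It is also fair to say that the biases in (b) and (c), 0.02 to 0.13 SD, are smaller than the simulated standard errors of about 0.13 to 0.19, and that this is a pilot. That limits the urgency, but a better method is available at almost no cost.

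**Conclusion.** The point holds as a defect in the analysis choice. The named method, as classically run, deletes incomplete patients; the plan supplies no rule that would prevent this, and usable W5 endpoints would be lost. Reading each phase as a separate record avoids the loss only by ignoring the pairing.

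The size depends on why patients leave. If dropout is unrelated to outcome, the cost is a small loss of precision. If it follows the Phase I endpoint, the completers' estimate ran from about 10% too small to about 29% too large. These percentages rest on assumed dropout rates, effect size and correlations; the documents give none of them. The firm figures are the 20% allowance implied by 50 and 40, and 35 completers if the rate were 30%.

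A likelihood model repairs loss that depends on observed scores. It does not repair departure of poor responders before a phase endpoint, as rule (d) shows, so it should not be presented as a complete cure.

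**What to change.** Replace the MANOVA with a linear mixed-effects model fitted by REML, one for each primary outcome. Fixed effects: treatment, period and sequence, with the screening score as covariate; the planned CAPS covariate can stay. Add a random patient effect. Use all observed post-randomisation scores from every randomised patient, and state this as the analysis set.

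For the CAARS-S:S, include the interim visits with a visit term, so that patients without a phase endpoint still contribute. Let the treatment effect differ by visit, so that the end-of-phase contrast remains the target: W1 and W6 fall in the placebo lead-in and wash-out weeks, and W2 and W7 come early in treatment. For the same reason these visits recover only part of what is lost. The AAQoL-29 and BAARS-IV have one endpoint per phase, so less can be recovered for them.

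Keep the complete-case analysis as a sensitivity analysis, and add one for data not missing at random.

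The cost is analysis wording, with no new visits or patients. The downside is reliance on a missing-at-random assumption, which is weaker than what a complete-case MANOVA needs. The change should be fixed before the unblinding and analysis that C1 places after the crossover.
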